12.4.2. Healthcare worker questionnaire and focus group discussion

Approximately three key healthcare workers from each participating clinic will be asked to complete a short on-line questionnaire about their experience with LA CAB+RPV.

We will interview the key healthcare workers responsible for delivering the service at each clinic including the lead HIV/ID Consultant, the Clinical Nurse Specialist and Pharmacist or any other member of staff involved with the delivery of LA CAB+RPV. The interview / focus group can take place at any time point during the study site participation in the study. An on-line consent process will be completed prior to any focus group taking place. Personal data will be anonymised.

12.5. Safety reporting

If a serious adverse event (SAE) has occurred during the participant follow up period and the SAE is possibly, probably or definitely related to LA CAB+RPV (i.e. a suspected serious adverse reaction) it should be reported to the ViiV safety team as soon as possible in the interest of pharmacovigilance. The definition of possible, probable or definitely related events is shown below.

12.5.1. Assessing adverse events for seriousness, causality and expectedness of adverse events

A serious adverse event is any untoward medical occurrence that meets one of the following criteria:

- 1. fatal
- 2. immediately life-threatening
- 3. results in hospitalisation or a prolongation of an existing hospitalisation (does not include visits to A+E without admission, admissions for social reasons or elective procedures for cosmetic surgery).
- 4. abnormal pregnancy outcome
- 5. causes severe disability/incapacity

The causality of the SAE should be assessed when deciding whether to report the SAE to ViiV. If any doubt exists please discuss with the site Principal Investigator.

Causality of adverse events							
Unrelated	No evidence of any causal relationship						
Unlikely	There is little evidence to suggest there is a causal relationship (e.g. the event did not occur within a reasonable time after a study procedure). There is another reasonable explanation for the event (e.g. the patient's clinical condition, other concomitant treatment).						
Possible	There is some evidence to suggest a causal relationship (e.g. because the event occurs within a reasonable time after a study procedure). However, the influence of other factors may have contributed to the event (e.g. the patient's clinical condition, other concomitant treatments).						
Probable	There is evidence to suggest a causal relationship with study procedures and the influence of other factors is unlikely.						

Definite	There is clear evidence to suggest a causal relationship with study
	procedures and other possible contributing factors can be ruled out.

Expectedness of the event in relation to LA CAB/RPV or underlying disease (HIV or associated comorbidities) must then be determined. Expected side effects from the product are listed in the summary of medical product characteristics (SmPC)

(https://viivhealthcare.com/content/dam/cf-viiv/viiv-healthcare/en_GB/medicines/CABENUVA-VOCABRIA-PM-26-Mar-2021.pdf).

If an SAE is deemed to be related to LA CAB/RPV and unexpected according to the SmPC then is a suspected unexpected serious adverse reaction (SUSAR), which requires expedited reporting and a high level of scrutiny.

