9.2. Secondary Objectives

2. ACCEPTABILITY:

- a. To explore the acceptability of LA CAB+RPV amongst PLWH and health care workers delivering the regimen through a participant questionnaire, healthcare practitioner questionnaire and qualitative research.
- b. To compare patient-reported outcomes including quality of life, treatment satisfaction and treatment preference in those on LA CAB+RPV compared to those who remain on oral ART (demographically similar but not eligible for LA ART)

3. FEASIBILITY:

- c. To describe the feasibility of using the regimen from a clinical and patient perspective through outcomes in the participant and healthcare practitioner questionnaires
- d. To explore barriers and facilitators to effective implementation of the LA CAB+RPV regimen
- **4. FIDELITY:** To describe the fidelity of regimen delivery and associated monitoring compared to intended use in BHIVA guidelines

5. EFFECTIVENESS:

e. To characterise the UK-wide population who are switched to LA CAB+RPV and indications for switch

- f. To describe virological and clinical outcomes at one year of therapy in those on LA CAB+RPV and in those remaining on oral ART (demographically similar but not eligible for LA ART)
- g. To identify where actionable adjustments to implementation can be made to optimise overall adoption, sustainability and effectiveness of LA CAB+RPV

10. Outcome Measures

There are no interventional components to the study. Service-specific approaches to implementation of LA CAB+RPV in use at the study sites at study outset will be described, contrasted and compared.

Objective	Outcome measures	
Implementation outcomes		
ADOPTION 1. To quantify the adoption cascade	 a. Proportion of clinical cohort eligible for LA CAB+RPV according to BHIVA guidance b. Proportion of eligible adults offered/discussed a switch to LA CAB+RPV c. Proportion who accept the switch to LA CAB+RPV d. Proportion who remain on LA CAB+RPV at one year and reasons for switching off the regimen 	

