 - Note: In general, hospitalisation signifies that the subject has been detained (usually involving at least an overnight stay) at the hospital or emergency ward for observation and/or treatment that would not have been appropriate in the physician's office or out-patient setting. Complications that occur during hospitalisation are AEs. If a complication prolongs hospitalisation or fulfils any other serious criteria, the event is 'serious'.

When in doubt as to whether 'hospitalisation' occurred or was necessary, the AE should be considered 'serious'. Hospitalisation for elective treatment of a preexisting condition that did not worsen from baseline is not considered an AE.

- d) results in disability/incapacity, or
 - Note: The term disability means a substantial disruption of a person's ability to conduct normal life functions. This definition is not intended to include experiences of relatively minor medical significance such as uncomplicated headache, nausea, vomiting, diarrhoea, influenza, and accidental trauma (e.g., sprained ankle) which may interfere or prevent everyday life functions but do not constitute a substantial disruption.
- e) is a congenital anomaly/birth defect.
- f) other.
 - Medical or scientific judgement should be exercised in deciding whether reporting is appropriate in other situations, such as important medical events that may not be immediately life-threatening or result in death or hospitalisation but may jeopardise the subject or may require medical or surgical intervention to prevent one of the other outcomes listed in the above definition. These should also be considered serious.
 - Examples of such events are invasive or malignant cancers, intensive treatment in an emergency room or at home for allergic bronchospasm, blood dyscrasias or convulsions that do not result in hospitalisation, or development of drug dependency or drug abuse.
- g) possible drug-induced liver injury

Version 01.00 - 09 DEC 19 (SAE Paper Back-up Form)]

SERIOUS ADVERSE EVENTS (SAE) (Page 3 of 4) INVESTIGATOR INSTRUCTIONS

MITEOTICATOR MOTROCHO	
SECTION 4	If deliberate or inadvertent administration of further dose(s) of study treatment(s) to the subject occurred, did the reported adverse
	event recur?
If Study Treatment was Stopped, Did the	
Reported Event(s) Recur After Further	
Study Treatment(s) Were Administered?	

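### The 12.5.1 causality table grades SAEs against study procedures although 12.5 triggers reporting on relatedness to LA CAB+RPV, and 12.5.1 and the reporting form define seriousness differently

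*Protocol*

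**What the plan says.** **Causality.** Protocol section 12.5 asks for a report to the manufacturer's safety team when "the SAE is possibly, probably or definitely related to LA CAB+RPV". It then says: "The definition of possible, probable or definitely related events is shown below". Section 12.5.1 confirms that the grade drives the decision: "The causality of the SAE should be assessed when deciding whether to report the SAE to ViiV". The table that follows has five grades. For *Probable* it says: "There is evidence to suggest a causal relationship with study procedures and the influence of other factors is unlikely". *Definite* is worded against the same thing. *Unlikely* and *Possible* mention timing after a study procedure as an example, and *Unrelated* names no exposure.

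On the nature of the study, section 10 says "There are no interventional components to the study", and section 13.1 adds that no drug is being tested and that participants' care is not altered.

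**Seriousness.** Section 12.5.1 lists five criteria. Its hospitalisation criterion leaves out A+E attendances that do not lead to admission. The SAE form in Appendix 22.2 carries its own list, a to g. Item f covers "important medical events that may not be immediately life-threatening or result in death or hospitalisation but may jeopardise the subject", with intensive emergency-room treatment among its examples. Item g is "possible drug-induced liver injury".

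**The concern.** The reporting rule and the scale it relies on name different exposures. The rule asks whether the drug caused the event. The scale, in the two grades that state an exposure outright, asks whether study procedures did. An assessor who follows the definitions as written is answering a different question from the one that 12.5 poses.

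Seriousness has a similar fault. It is defined twice, and the two definitions do not select the same events. Under 12.5 only an SAE is reported, so the 12.5.1 list is applied before anyone opens the form. Where it is the narrower of the two, it decides.

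What is at stake is consistent safety reporting across about 10-12 clinics (section 11.2). Section 12.5.2 sets a 24-hour reporting deadline and requires SUSARs to reach the ethics committee within 15 days. Section 15.1.4 gives failure to meet safety reporting requirements as an example of a serious breach. Sites therefore need one rule that they can follow as written.

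**Working it through.** No arithmetic applies beyond counting. The check sets the texts side by side.

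**1. What each causality grade is anchored to (table in 12.5.1)**

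| Grade | Reportable under 12.5? | Exposure named |
|---|---|---|
| Unrelated | No | None |
| Unlikely | No | Study procedure, as an example only |
| Possible | Yes | Study procedure, as an example only |
| Probable | Yes | Study procedures, in the definition |
| Definite | Yes | Study procedures, in the definition |

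Two of five grades are defined against study procedures, two of five mention one by example, and one of five names nothing. None of the five names LA CAB+RPV.

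**2. Whether the injections can count as study procedures.** They cannot on the protocol's own account. Sections 10 and 13.1 rule out any intervention or drug testing. Section 12.2 places consent before any study procedure, yet sections 11.2.1 and 12.3.1 admit people who switched up to 6 months before their site opened. For them the injections began before any study procedure could have taken place. What the study itself does is obtain consent, extract records, and run questionnaires and interviews.

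**3. Literal consequence.** Since the injections are not study procedures, a reaction to them cannot satisfy the wording of *Probable* or *Definite*. The highest grade open to it is *Possible*.

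The reporting line falls between *Unlikely* and *Possible*. At that line the only timing example in either row is the interval since a study procedure. An event soon after an injection but long after a questionnaire matches the timing example under *Unlikely*. Both rows also give concomitant treatment as a competing explanation, and an assessor could take that to include the routine-care injections. Either reading pulls the grade down, though neither is forced.

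**4. What the rest of the protocol uses.** Section 12.3.2 ties the same three grades to the injections. Section 12.5 and the SUSAR rule in 12.5.1 tie relatedness to LA CAB+RPV. The form asks about study treatment. The table is the exception, and it is also the designated definition.

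**5. Seriousness criteria**

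| Form, Appendix 22.2 | Section 12.5.1 |
|---|---|
| a Death | Present |
| b Life-threatening | Present |
| c Hospitalisation or prolongation | Present, with different limits |
| d Disability or incapacity | Present |
| e Congenital anomaly | Worded differently (abnormal pregnancy outcome) |
| f Other important medical events | No counterpart |
| g Possible drug-induced liver injury | No counterpart |

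Two of the form's seven items have no counterpart. The limits on hospitalisation also differ: the form counts being detained on an emergency ward, while 12.5.1 sets aside A+E visits without admission.

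As an example, take a convulsion treated in an emergency room, with no admission, not immediately life-threatening and leaving no severe disability. It meets item f on the form and none of the five criteria in 12.5.1. It is not an SAE under 12.5.1, so the form need never be opened.

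**The case against.** The strongest reply is that nobody would be misled. Sections 12.3.2 and 12.5, the SUSAR rule and the form all point to the treatment. Section 12.5.1 sends doubtful cases to the site Principal Investigator, and 12.5.2 gives reporting to the participant's responsible clinician.

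Much of this stands, and it limits the consequence. A reader might infer that a genuine drug reaction would be graded *Unrelated* and never sent. The documents do not support that. *Unrelated* requires no evidence of any causal relationship and names no exposure. *Possible* needs only some evidence, mentions a study procedure only as an example, and is reportable.

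A reader might also infer that the study's counts of related events will be too low. That is not shown. Table 1 collects interim medical events at months 6 and 12 whether or not an SAE report is made, 12.3.2 has them graded against the injections, and no outcome in section 10 is a count of related SAEs. One reservation remains: 12.3.2 gives no definitions of its own, so the table's ambiguity could carry over into that data item.

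On seriousness, 12.5.1 does cover fatal, life-threatening and disabling events and abnormal pregnancy outcomes without hospitalisation, so it would be wrong to say that every non-hospitalised serious event is missed. The form is a generic template with randomisation and blinding fields, and nothing in the protocol says that its list overrides 12.5.1. That is a reason to reconcile the two, not to assume that either governs.

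The reply does not remove the defect. To reach the intended result, an assessor has to set aside the stated definition.

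**Conclusion.** The point holds as two wording conflicts in the safety section.

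- **Causality:** the table's anchor contradicts 12.3.2, 12.5 and the SUSAR rule. Read literally, a reaction to LA CAB+RPV cannot be graded above *Possible*. The supportable consequence is inconsistent or under-graded causality between sites, with some risk of under-reporting at the *Unlikely*/*Possible* line.
- **Seriousness:** two of the form's seven criteria are absent from 12.5.1, and emergency-room care without admission is treated differently. An event can be serious on the form and screened out before the form is used.

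This rests on reading the table as the operative definition, as 12.5 says it is, and on treating routine-care injections as outside study procedures, as sections 10 and 13.1 imply. The documents give no basis for estimating how many events would be affected. No sample size, error rate or listed outcome changes.

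**What to change.** 1. In the 12.5.1 table, replace the references to a study procedure or study procedures with LA CAB+RPV, to match 12.5. A line stating that study treatment on the form means LA CAB+RPV would align the form as well.
2. Reconcile the seriousness list in 12.5.1 with items a to g on the form, including the handling of emergency-room care without admission, so that one definition applies in both places.

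The cost is an amendment to one table and one list, with the approvals that any amendment needs. The downside is that a few more events may need reporting. Design, sample size and treatment are unaffected.

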12.5.2. Reporting of SAEs and SUSARs

With the support of the local research team, the SAE reporting process should be performed by the **participant's responsible clinician** who is likely to have the best understanding of the participant's medical history, the event and its clinical course. The safety reporting form is in Appendix 21.5. It should be reported to ViiV and the Sponsor within 24 hours of the site research team becoming aware of the event. Pregnancies arising on cabotegravir and rilpivirine should also be notified to ViiV within 7 days of awareness of pregnancy. The pregnancy notification form will be provided by the coordinating centre if required. The email address for notifications are:

Sponsor: [contact], [contact]

ViiV: [contact]

SUSARs should be reported as above but also require reporting to the research ethics committee (REC) within 15 days. This would be handled by the Sponsor.

12.6. Registry dataset to quantify the adoption cascade

Participating clinics will be asked to perform a local database search and create a registry dataset of all participants eligible for the LA CAB+RPV regimen according to the BHIVA guidance, or who have already commenced the LA regimen. From this registry dataset, over the following 12 months, the clinic will then quantify the number ever offered a switch to LA CAB+RPV, the number who accept the switch and the number who remain on the regimen for at least 1 year duration. Reasons for not being offered or declining a switch to LA CAB+RPV will be recorded.

13. Risks and benefits for participants

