11.1.1. Observational study using routinely collected clinic data

The study will capture data from HIV-1 positive adults receiving long-acting cabotegravir and rilpivirine as part of their treatment regimen. All HIV-1 positive adults (≥ 16 years) who initiated long-acting cabotegravir and rilpivirine-based ART any time from 6 months prior to study site initiation will be eligible to be included in this study. A demographically similar comparator group on oral ART will also be invited to join the study. Routinely collected medical data from eligible and consenting participants' medical records will be extracted at key intervals, as laid out in the Schedule of Activities (see section 12.3.4), and entered into an electronic data capture system (Research Electronic Data Capture, REDCap). Variables of interest include demographic data, HIV treatment history, laboratory findings, which are all collected routinely in line with the BHIVA monitoring guidelines.

The total duration of patient follow-up is at least 1 year from the time of enrolment. The final analysis will be conducted following database lock after the last study participant has reached the 12 months treatment milestone and all data queries have been resolved.

Patients who received LA ART outside of the BHIVA criteria e.g. on compassionate grounds are of interest and can be included in the prospective study; the reasons for BHIVA criteria ineligibility and outcomes (duration of therapy, virological and clinical) will be described.

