11.1.5. Notes review to understand adoption cascade

A registry dataset of patients eligible for LA CAB/RPV will be generated from the main clinic database. Over the following 12 months, the clinic will then quantify the number of patients ever offered a switch to LA CAB+RPV, the number who accept the switch and the number who remain on the regimen for at least 1 year duration. Reasons for not being offered or declining a switch to LA CAB+RPV will be recorded.

[figure not shown]

Figure 2. Schematic of study including qualitative and quantitative aspects

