The number and proportion of participants who discontinue LA CAB+RPV and the reason for discontinuation will be described.

The 'end of study' is the point at which last participant final visit individual data has been entered into the electronic data capture system and all the qualitative work has been completed. Thereafter, the 'end of study' the close out visit will be performed. The study will only be considered 'closed' when all participants have completed their final study visit, all assessments completed, all the data have been entered into the database and all data queries resolved, close out visit conducted, the database locked and data analysis performed and reports written.

18. Study Management and Oversight

The study has undergone independent peer review at the Protocol Review Panel at University of Sussex.

The study will be managed via the Brighton and Sussex Medical School Department of Global Health and Infection at the University of Sussex. The study management group (SMG) consisting of the Chief Investigators, Co-Investigators, Study Manager, Data Manager will be responsible for the day-to-day conduct of the study and will troubleshoot any operational issues.

As this is a low-risk non-interventional protocol, there is no requirement for a data safety monitoring committee for this study. University of Sussex safeguarding policies will be followed https://www.sussex.ac.uk/safeguarding/.

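### The registry counts offers, acceptances and one-year retention in a single 12-month window, so it cannot observe one-year retention in anyone who switches during that window

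*Protocol*

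**What the plan says.** The protocol summary (section 6) and the outcome table (section 10) both list, as the fourth adoption outcome, "Proportion who remain on LA CAB+RPV at one year and reasons for switching off the regimen". Adoption is the primary objective, so this is primary outcome 1d. Section 9.1, which words the primary objective in full, ends the cascade at acceptance of the switch.

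The data for the cascade come from a clinic registry. Section 12.6 says: "From this registry dataset, over the following 12 months, the clinic will then quantify the number ever offered a switch to LA CAB+RPV", and continues in the same sentence with "the number who accept the switch and the number who remain on the regimen for at least 1 year duration". Section 11.1.5 sets the same period: "Over the following 12 months, the clinic will then quantify the number of patients ever offered a switch to LA CAB+RPV". Neither section states a later status check. Section 12.6 also admits to the registry those "or who have already commenced the LA regimen", with no limit on how early they began. The reasons that the registry is told to record are those for not being offered a switch and for declining one.

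The prospective cohort runs on a different clock. Section 11.1.1 says: "The total duration of patient follow-up is at least 1 year from the time of enrolment", and "The final analysis will be conducted following database lock after the last study participant has reached the 12 months treatment milestone". Section 17 adds: "The number and proportion of participants who discontinue LA CAB+RPV and the reason for discontinuation will be described". The protocol does not say whether 1d is to be taken from the registry or from the cohort.

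**The concern.** Offer and acceptance are events that a 12-month window can capture. Remaining on the regimen for a year is a duration, and it needs 12 months after each person's own start. The registry applies one calendar window to all three counts, so the patients whose offer and acceptance it observes prospectively are the ones whose retention it cannot observe.

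What a clinic following the text would report depends on how it treats those patients. If they stay in the denominator as acceptors without a completed year, the retention proportion is too low. If they are left out, the last step describes only people who started before the registry existed, while the offer and acceptance steps describe a wider group. These earlier starters may be a more selected group, and the steps of the cascade then no longer follow the same people.

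A statistical analysis plan cannot repair this alone. It can define a denominator or a censoring rule, but it cannot supply 12-month status that the clinics were never asked to collect.

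**Working it through.** The protocol gives no sample size or retention figure for the registry, so there is no stated number to reproduce. The check is follow-up arithmetic.

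**Inputs from the protocol**
- Registry window: 12 months from creation (11.1.5, 12.6).
- Retention criterion: at least 1 year on the regimen (12.6).
- Registry membership includes patients already on the regimen (12.6).
- Cohort month-12 tolerance: ± 2 months (Table 1, 12.3.4).
- Site duration: 2 years (section 6).
- Cohort size on LA CAB+RPV: minimum 150 (section 17).

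**Formula.** Let t be the switch month relative to registry creation and W the month of the last status check. Possible time on the regimen is W − t. A patient can be assessed for one-year retention only if W − t ≥ 12.

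**As written, W = 12**
- Switch after creation (0 < t ≤ 12): 12 − t is below 12, so 0% can be assessed. Only a switch on the day of creation reaches exactly 12. This result does not depend on the uptake pattern.
- If switches are spread evenly over the window (assumption), mean possible follow-up is 12 − 6 = 6 months.
- Start before creation (t < 0): 12 − t exceeds 12, so all can be assessed. For starts in months −6 to 0 the range is 12 to 18 months.
- Mixed starts: the assessable share equals the share s who started before creation. The protocol does not give s, so any value from 0% to 100% is possible. As an illustration, a constant start rate over months −6 to 12 gives s = 6/18 = 33%.

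**Size of the downward bias.** If r is the true one-year retention and in-window switchers are all counted as not retained, the reported proportion is r × s. The shortfall is therefore set by s, which is unknown.

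**Does a tolerance rescue it?** Accepting 10 months as one year requires 12 − t ≥ 10, so t ≤ 2. Letting the cut slip to month 14 requires 14 − t ≥ 12, again t ≤ 2. With even uptake, either gives 2/12 = 17% of in-window switchers. Section 12.3.4 sets this tolerance for cohort visits, not for the registry.

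**With a later look-up, W = 24.** For t from 0 to 12, 24 − t runs from 12 to 24 months, so the assessable share of in-window switchers goes from 0% to 100%. If the registry is created k months after the site opens, the last look-up falls at site month 24 + k. It fits the 2-year site duration only when k = 0.

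**What the cohort can give.** With n = 150, the 95% half-width for one-year retention is 1.96 × √(p(1 − p)/150). This is 6.4, 4.8 and 3.5 percentage points for assumed retention of 80%, 90% and 95%.

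**The case against.** The strongest reply is that one-year retention is measured elsewhere. The cohort follows every LA participant for at least a year, is analysed only after the last one reaches 12 months of treatment, and reports discontinuations with reasons. Outcome 1d asks for reasons for coming off the regimen, which the registry text does not collect and section 17 does, so the cohort may be meant to supply at least part of 1d. The registry also holds earlier starters, all of whom can reach 12 months by the end of the window.

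This stands against the inference that 1d cannot be estimated at all, which a reader might draw from the window arithmetic. The documents do not support that inference. It would also be wrong to say that the study has no per-patient 12-month clock: Table 1 has one, and sets the baseline of earlier switchers at their switch date. That criticism applies to the registry sections only.

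The reply does not restore the clinic-level cascade. Section 9.1 defines the cascade on each clinic cohort. The observational cohort is a consented sample, planned at roughly 10–20 LA patients per centre with possible oversampling at larger centres (11.2). It admits people up to 6 months after switching, who must then be reached for consent, which may favour those still on treatment. Sections 11.1.5 and 12.6 assign the retention count to the registry.

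A reader might also infer a large numerical error in 1d. The documents do not support a figure: they give neither the share of earlier starters nor a rule for counting patients who have not reached 12 months. Section 7 says that roll-out was under way, so earlier starters may not be few. The absence of a censoring rule is not a fault here, because section 17 leaves analysis detail to the analysis plan. The Gantt bars are not shown, so the planned registry dates cannot be checked.

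**Conclusion.** The point holds for the registry. As sections 11.1.5 and 12.6 are written, none of the patients who switch during the 12-month window can be observed for one year on the regimen. The whole-clinic form of 1d is therefore either restricted to patients who started before registry creation or, if later switchers stay in the denominator as not retained, biased downwards. The 0% rests only on the stated window and criterion. The 6-month mean and the 17% assume even uptake, and the 33% assumes a constant start rate from 6 months before creation. The size of any bias in 1d cannot be calculated from the protocol.

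Severity is moderate. A primary outcome is affected and its source is left unstated, but the study is descriptive, a separate cohort estimate exists, and the repair is small.

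**What to change.** In sections 11.1.5 and 12.6:

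1. Keep the 12-month window for counting offers and acceptances.
2. For every registry patient who starts LA CAB+RPV, record whether they are still on it 12 months after their own switch date, with the stop date and the reason for stopping. The reason is needed for 1d and is not on the registry's present list.
3. State whether 1d comes from the registry or the cohort, its denominator and its cut-off. If both are reported, label the cohort figure as a separate estimate in a consented sample.
4. Create the registry at site opening, so that look-ups running to month 24 fit the 2-year site duration.

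If the later look-up is not feasible, limit the 1d denominator to patients with 12 months of possible follow-up, and say that it then describes those who started before registry creation. How retention is estimated can stay with the analysis plan; a fixed 12-month status for each starter is enough for a proportion.

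The cost is protocol wording, one further record look-up per starter and a later registry cut-off. No extra patients or visits are needed.
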